### 6.5.3. Dose modification and toxicity management of infusion-reactions related to pembrolizumab

Pembrolizumab may cause severe or life threatening infusion-reactions including severe hypersensitivity or anaphylaxis. Signs and symptoms usually develop during or shortly after drug infusion and generally resolve completely within 24 hours of completion of infusion. Dose modification and toxicity management guidelines on pembrolizumab associated infusion reaction are in [Table 6](#).

CCI - This section contained Clinical Outcome Assessment data collection questionnaires or indices, which are protected by third party copyright laws and therefore have been excluded.

CCI - This section contained Clinical Outcome Assessment data collection questionnaires or indices, which are protected by third party copyright laws and therefore have been excluded.

## 6.6. Blinding

This is an open-label study.

## 6.7. Packaging and labelling/Preparation/Handling/Storage

The contents of the label will be in accordance with all applicable regulatory requirements.

Open label vials of belantamab mafodotin solution 20 mg/mL, 1.5 mL, each carton contains 1 x vial.

Open label vials of pembrolizumab solution (100 mg/4 mL), each carton contains 1 x vial.

### 6.7.1. Belantamab Mafodotin

#### *Preparation*

Belantamab mafodotin Solution for Infusion, 20 mg/mL, 1.5 mL is supplied as a frozen liquid. Before use, thaw each vial of belantamab mafodotin and prepare infusion solution. Refer to the SRM for further details on preparation of belantamab mafodotin.

#### *Handling*

Under normal conditions of handling and administration, investigational product (IP) is not expected to pose significant safety risks to site staff. A Material Safety Data Sheet (MSDS) describing the occupational hazards and recommended handling precautions will be provided to site staff if required by local laws or will otherwise be available from GSK upon request.

In the case of unintentional occupational exposure notify the study monitor, the GSK Medical Monitor and/or the study manager.

Refer to the SRM for detailed procedures for the disposal and/or return of unused study treatment(s).

#### *Administration*

Belantamab mafodotin is compatible with polyvinylchloride-lined or polyolefin-lined intravenous infusion administration sets, 0.2 micron polyethersulfone filters, or optionally a polyurethane catheter. Doses of belantamab mafodotin are to be administered as an IV infusion via an infusion pump that can ensure precision to the decimal point of a mL for the infusion rate at lower doses. It is recommended to prime the IV tubing with at least 15 mL prior to dosing.

***Storage***

Belantamab mafodotin must be stored in a secure area under the appropriate physical conditions for the product. Access to and administration of the belantamab mafodotin will be limited to the investigator and authorized site staff. Belantamab mafodotin must be dispensed or administered only to subjects enrolled in the study and in accordance with the protocol.

Belantamab mafodotin is to be stored at a temperature range of -50°C to -15°C. Maintenance of a temperature log is required.

**6.7.2. Pembrolizumab*****Preparation***

Pembrolizumab will be provided in a single-use vial at 100 mg/4 mL (25 mg/mL).

Preparation for intravenous infusion: withdraw the required volume from the vials of pembrolizumab and transfer into an intravenous (IV) bag containing 0.9% sodium chloride injection, USP or 5% dextrose injection, USP. The final concentration of the diluted solution should be between 1 mg/mL to 10 mg/mL. Refer to the SRM for further details on preparation of pembrolizumab.

***Handling***

Under normal conditions of handling and administration, investigational product (IP) is not expected to pose significant safety risks to site staff. A Material Safety Data Sheet (MSDS) describing the occupational hazards and recommended handling precautions will be provided to site staff if required by local laws or will otherwise be available from GSK upon request.

In the case of unintentional occupational exposure notify the study monitor, the GSK Medical Monitor and/or the study manager.

Refer to the SRM for detailed procedures for the disposal and/or return of unused study treatment(s).

***Administration***

Pembrolizumab infusion solution should be intravenously administered over 30 minutes through an intravenous line containing a sterile, non-pryogenic, low-protein binding 0.2 micron to 5 micron in-line or add-on filter. However, given the variability of infusion pumps from site to site, a window between -5 minutes and +10 minutes is permitted (i.e., infusion time is 30 minutes -5 min/+10 min).

***Storage***

The vials of pembrolizumab (100 mg/4 mL) solution should be stored under refrigeration at 2-8°C (36-46°F) in original carton to protect from light. Do not freeze and do not shake.

**6.8. Product Accountability**

In accordance with local regulatory requirements, the investigator, designated site staff, or head of the medical institution (where applicable) must document the amount of investigational product (IP) and other study treatments dispensed and/or administered to study subjects, and the amount received from and returned to GSK, when applicable. Product accountability records must be maintained throughout the course of the study. Refer to the SRM for further detailed instructions on product accountability.

**6.9. Compliance with Study Treatment Administration**

Both study drugs: belantamab mafodotin and pembrolizumab will be administered intravenously to subjects at the study site. The dose of pembrolizumab will be 200 mg. The dose of belantamab mafodotin is based on body weight calculation, and will be escalated from 2.5 mg/kg to 3.4 mg/kg in Part 1. The dose of GSK1857916 in Part 2 will be the RP2D as established in Part 1. The dose of belantamab mafodotin may be reduced for toxicity according to protocol guidelines.

**6.10. Treatment of Investigational Product Overdose**

Selected non-serious and serious adverse events are also known as Events of Clinical Interest (ECI) and must be reported to the sponsor within 24 hours of awareness.

Events of clinical interest for this trial include:

1. an overdose of Sponsor's product, as defined below – Treatment of Overdose, that is not associated with clinical symptoms or abnormal laboratory results.
2. an elevated AST or ALT lab value that is greater than or equal to 3X the upper limit of normal and an elevated total bilirubin lab value that is greater than or equal to 2X the upper limit of normal and, at the same time, an alkaline phosphatase lab value that is less than 2X the upper limit of normal, as determined by way of protocol-specified laboratory testing or unscheduled laboratory testing.\*

\*Note: These criteria are based upon available regulatory guidance documents. The purpose of the criteria is to specify a threshold of abnormal hepatic tests that may require an additional evaluation for an underlying etiology. The trial site guidance for assessment and follow up of these criteria can be made available. It may also be appropriate to conduct additional evaluation for an underlying etiology in the setting of abnormalities of liver blood tests including AST, ALT, bilirubin, and alkaline phosphatase that do not meet the criteria noted above. In these cases, the decision to proceed with additional evaluation will be made through consultation between the study investigators and the Sponsor Clinical Director. However, abnormalities of liver blood tests that do not meet the criteria noted above are not ECIs for this trial.

For this study, an overdose of pembrolizumab will be defined as 1000 mg or  $\geq 5$  times the indicated dose. No specific information on the treatment of overdose of pembrolizumab and belantamab mafodotin.

In the event of an overdose (defined as administration of more than the protocol-specified dose) of belantamab mafodotin and pembrolizumab, the investigator should:

- contact the GSK Medical Monitor immediately
- closely monitor the subject for adverse events (AEs)/serious adverse events (SAEs) and laboratory abnormalities until belantamab mafodotin can no longer be detected systemically (at least 3 months)
- obtain a plasma sample for pharmacokinetic (PK) analysis within 24 hours of the event if requested by the GSK Medical Monitor (determined on a case-by-case basis)
- document the quantity of the excess dose as well as the duration of the overdosing in the eCRF

## 6.11. Lifestyle and/or Dietary Restrictions

### 6.11.1. Contraception

Belantamab mafodotin and pembrolizumab may have adverse effects on a fetus in utero. The cytotoxic component of belantamab mafodotin, MMAF, disrupts microtubule function, is genotoxic, and can be toxic to rapidly dividing cells, suggesting it has the potential to cause embryotoxicity and teratogenicity and should not be administered to pregnant or lactating women [[GlaxoSmithKline Document Number 2013N175128\\_09, 2021](#)]. Furthermore, it is not known if pembrolizumab has transient adverse effects on the composition of sperm. Subjects should be informed that taking the study medication may involve unknown risks to the fetus (unborn baby) if pregnancy were to occur during the study.

#### 6.11.1.1. Female Subjects

In order to participate in the study, WOCBP must adhere to the contraception requirement (from the day of study medication initiation) during the study and for 9 months after the last dose of study treatment. If there is any question that a WOCBP will not reliably comply with the requirements for contraception, that subject should not be entered into the study. Full details are in [Appendix 8](#).

#### 6.11.1.2. Male Subjects

Male subjects with female partners of child bearing potential must comply with the contraception requirements highlighted in Section [5.1](#) from the time of first dose of study medication until 140 days after the last dose of belantamab mafodotin. Details on contraceptive options for subjects with a partner of childbearing potential are in [Appendix 8](#).

Men with a pregnant or breastfeeding partner must agree to remain abstinent from penile-vaginal intercourse or use a male condom during each episode of penile penetration from the time of first dose of study until 6 months after the last dose of study treatment to allow for clearance of any altered sperm.

#### 6.11.1.3. Lactation Restrictions

Female subjects who are lactating must discontinue nursing prior to the first dose of study treatment and must refrain from nursing throughout the treatment period and for 4 months following the last dose of study treatment.

### 6.11.2. Subjects with Contact Lenses

Contact lenses are prohibited while on the study treatment (from first dosing to the end of study treatment). Contact lens use may be restarted after the ophthalmologist (or an optometrist if an ophthalmologist is not available) confirms there are no other contraindications.

Use of bandage contact lenses is permitted during study treatment as directed by the treating ophthalmologist (or optometrist if an ophthalmologist is not available).

## **6.12. Concomitant Medications/Vaccinations and Non-Drug Therapies**

Subjects will be instructed to inform the investigator prior to starting any new medications from the time of first dose of study treatment until the end of the treatment visit. Any concomitant medication(s), including non-prescription medication(s) and herbal product(s), taken during the study will be recorded in the eCRF. Additionally, a complete list of all prior anti-cancer therapies will be recorded in the eCRF.

If future changes are made to the list of permitted/prohibited medications, formal documentation will be provided by GSK and stored in the study file. The SRM will be updated to include this information. Any such changes will be communicated to the investigative sites in the form of a letter.

### **6.12.1. Permitted Medication(s)**

Subjects should receive full supportive care during the study, including transfusion of blood products, growth factors, and treatment with antibiotics, anti-emetics, antidiarrheals, and analgesics, as appropriate.

Concomitant therapy with bisphosphonates and RANKL inhibitors are allowed.

Subjects may receive local irradiation or elective surgery, eg. for pain control after discussion with the medical monitor.

### **6.12.2. Tumor Lysis Syndrome (TLS) Prevention and Treatment Recommendations**

Subjects with a high tumor burden with a high proliferative rate might be at risk for TLS and should be monitored for clinical and laboratory signs of tumor lysis. Specifically, all subjects with elevated uric acid ( $>8$  mg/dL, or  $>476$  mmol/L) should receive prophylaxis with allopurinol, or rasburicase. All subjects should be hydrated to reduce risks for renal toxicity and tumor lysis syndrome (TLS) with belantamab mafodotin treatment. Adequate fluid volume status should be maintained throughout treatment and blood chemistries should be monitored as indicated in the Time and Events Tables in Section 7 or more frequently if clinically indicated. Prior to the first dose in Cycle 1, all subjects should receive at least 250- 500 mL of intravenous normal saline or other appropriate intravenous fluid. Additionally, 250-500 mL of intravenous fluid should be given as needed following belantamab mafodotin administration. Intravenous hydration should be continued, as needed, in subsequent cycles and subjects should be monitored for fluid overload during this period.

If the constellation of clinical and/or laboratory signs tested on Cycle 2 Day 1 indicates a possibility of developing TLS, subjects should be hospitalized with frequent monitoring of clinical signs and clinical chemistries and treated accordingly.

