#### **2.2.5.1. Pharmacokinetics and Pharmacodynamics**

The pharmacokinetics and pharmacodynamics of belantamab mafodotin (antibody-drug conjugate, including complex with soluble BCMA (sBCMA)) and total monoclonal antibody (total mAb; including complex), and cys-mcMMAF were investigated in 291 participants with RRMM following IV administration at doses from 0.03 to 4.6 mg/kg Q3W in Study BMA117159 (n=73) and at doses of 2.5 or 3.4 mg/kg Q3W in Study 205678 (n=218).

Maximum concentrations (Cmax) of belantamab mafodotin and total monoclonal antibody were observed at or shortly after the end of infusion (EOI), while cys-mcMMAF Cmax values were generally observed on Day 2. On a molar basis, plasma concentrations of cys-mcMMAF were <1% of belantamab mafodotin concentrations. There was limited accumulation (less than 2-fold) of belantamab mafodotin or cys-mcMMAF during subsequent cycles.

Belantamab mafodotin pharmacokinetics were well described by a linear, two compartment population model, with a time-varying decrease in clearance in a population pharmacokinetic analysis. At Cycle 1, belantamab mafodotin had a systemic clearance of 0.92 L/day, steady-state volume of distribution of 10.8 L, and an elimination half-life of 12 days in participants with RRMM in Study 205678. Over time, clearance was reduced by 28%, resulting into 0.72 L/day, with an elimination half-life of 14 days. The time to 50% change in clearance was approximately 50 days.

No clinically significant differences in the pharmacokinetics of belantamab mafodotin or cys-mcMMAF were observed based on age (34 to 89 years), sex, race (African American/Black and White), body weight (42 to 130 kg), mild or moderate renal

impairment (eGFR  $\geq 30$  mL/min/1.73m^2) or mild hepatic impairment (NCI-ODWG classification). Higher serum levels of  $\beta_2$ -microglobulin, IgG, and soluble BCMA (sBCMA) and lower levels of albumin are associated with more advanced multiple myeloma or a higher multiple myeloma disease burden. Higher baseline IgG and sBCMA levels, and lower baseline albumin levels were associated with higher belantamab mafodotin clearance leading to lower average and trough concentrations (Ctau) of belantamab mafodotin. Higher baseline IgG and sBCMA levels were associated with higher cys-mcMMAF central volume of distribution leading to lower cys-mcMMAF Cmax.

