#### **4.2.3.1. Dose-Limiting Toxicity Criteria (Part 1 only)**

Any subject in Part 1 who received at least one treatment cycle of belantamab mafodotin in combination with pembrolizumab will be evaluated for DLTs.

All toxicities will be graded using National Cancer Institute (NCI) CTCAE Version 4.03 [NCI, 2010]. In addition, for belantamab mafodotin treatment related corneal events, the GSK Grading Scale (Appendix 9) should be used for evaluation of DLT.

A DLT is defined as an AE that meets at least one of the criteria defined below and is considered by the investigator to be clinically relevant and attributed (definitely, probably, or possibly) to the study therapy during the 21 day DLT observation period.

- Any Grade 4 non-hematologic toxicity
- Any Grade 3 non-hematologic toxicity, with the following exceptions (i.e., the following will not be considered a DLT): Grade 3 diarrhea, nausea or vomiting that responds to standard of care within 72 hours; Grade 3 hypertension (controlled following addition of 1 antihypertensive medication); and Grade 3 tumor lysis syndrome
- Any Grade 3 or greater non-hematologic laboratory value if either:
  - The laboratory abnormality persists for >48 hrs despite supportive treatment or,
  - The abnormality leads to hospitalization
- Hematologic toxicity:
  - Grade 4 hematologic toxicity lasting  $\geq$  7 days, except thrombocytopenia:
    - Grade 4 thrombocytopenia of any duration
    - Grade 3 thrombocytopenia associated with clinically significant bleeding
  - Grade 3 or greater febrile neutropenia lasting >48 hours despite adequate treatment:

CCI - This section contained Clinical Outcome Assessment data collection questionnaires or indices, which are protected by third party copyright laws and therefore have been excluded.

- Nephrotoxicity requiring dialysis, and is not considered to be due to disease under study (i.e., myeloma) based on investigator's assessment
- Liver toxicity meeting pre-specified GSK liver stopping criteria (see Section 5.4.1.1)
- Prolonged delay (>14 days) in initiating Cycle 2 due to any treatment (pembrolizumab or belantamab mafodotin) related toxicity, with the exception of Grade 1-2 corneal events (GSK grading scale for belantamab mafodotin treatment related corneal events; Table 17)
- Any treatment-related toxicity that causes the subject to discontinue treatment during Cycle 1

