**Table 8 Time and Events Table: Part 1 and Part 2 – On Study Assessments Completed Independent of Dosing**

Study Assessments 	C1 Day 1 (Week 1)	C1 Day 8 (Week 2)	Treatment Period: Q3W from Wk 4 until EOT	Notes
Physical Exam	X		X	
Vital Signs (BP, HR, Body Temperature)	X 	X	X 	
Adverse Events 	Ongoing			
Concomitant Medications	Ongoing			
Genetics 	X			
ECOG Performance Status			X	
			Safety	
Ocular Exam			X 	
Hematology	X 	X 	X 	
Clinical chemistry	X 	X	X	
eGFR 	X 	X	X	
Urinalysis	X 		X	
CRP			X	

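### The uric acid trigger for tumor lysis prophylaxis (Section 6.12.2) is printed in two units that differ 1000-fold

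*Protocol*

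**What the plan says.** Section 6.12.2 of the protocol has a rule that begins "Specifically, all subjects with elevated uric acid" and gives the cut-off in parentheses in two units, above 8 mg/dL or above 476 mmol/L. The SI part and the action it triggers read "mmol/L) should receive prophylaxis with allopurinol, or rasburicase". Uric acid is listed with clinical chemistry in Table 11, so the rule will be read against results that the protocol itself collects.

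The same section asks for intravenous fluid before the first dose in Cycle 1. On monitoring it says that "blood chemistries should be monitored as indicated in the Time and Events Tables in Section 7 or more frequently if clinically indicated". Table 8 schedules clinical chemistry at Cycle 1 Day 1, at Cycle 1 Day 8, and every three weeks from Week 4. The section's only sentence on hospitalisation reads "If the constellation of clinical and/or laboratory signs tested on Cycle 2 Day 1 indicates a possibility of developing TLS, subjects should be hospitalized".

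**The concern.** A cut-off given in two units should describe one concentration, so that a site reaches the same decision whichever unit its laboratory reports. Here the two versions look incompatible by orders of magnitude. At stake is a safety instruction. A site that reports in SI units and applies the printed SI figure would never find a subject above it, while a site that reports in mg/dL would apply a working limit.

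A smaller matter is the visit named in the hospitalisation sentence. It refers only to Cycle 2 Day 1, although the section calls for fluid around the first dose and chemistry is already drawn twice in Cycle 1.

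**Working it through.** **Unit conversion.** Inputs:
- the conventional cut-off, 8 mg/dL, and the SI cut-off as printed, 476 mmol/L (both Section 6.12.2);
- the molar mass of uric acid, 168.11 g/mol, an assumption from outside the protocol, tried from 168.0 to 168.2.

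Formula: mmol/L = (mg/dL × 10) / molar mass in g/mol.

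1. 8 mg/dL × 10 = 80 mg/L.
2. 80 / 168.11 = 0.4759 mmol/L = 475.9 micromol/L. The plan's 476 is therefore not reproduced in mmol/L, but is reproduced to the nearest whole number in micromol/L.
3. Ratio of printed to converted limit: 476 / 0.4759 ≈ 1000.
4. Converted back: 476 × 168.11 / 10 = 8,002 mg/dL, or about 80 g/L.

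| Molar mass (g/mol) | 8 mg/dL in mmol/L | in micromol/L | 476 mmol/L ÷ converted limit |
|---|---|---|---|
| 168.0 | 0.4762 | 476.2 | 999.6 |
| 168.11 | 0.4759 | 475.9 | 1000.3 |
| 168.2 | 0.4756 | 475.6 | 1000.8 |

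The result does not depend on the exact molar mass.

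**A comparison within the protocol.** The albumin/creatinine limits are also given in two units: 500 mg/g with 56 mg/mmol (Table 3), and 2000 mg/g with 224 mg/mmol (Table 4). With a creatinine molar mass of 113.12 g/mol (again a constant from outside), 500 × 113.12 / 1000 = 56.6 and 2000 × 113.12 / 1000 = 226.2. Both agree with the printed values to about 1%. The uric acid discrepancy is of a different order and is not explained by loose rounding.

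**The visit reference.** No arithmetic error is involved, so the provisions are set side by side.

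| Provision | Timing stated |
|---|---|
| Intravenous fluid (6.12.2) | Before the first dose in Cycle 1; then as needed |
| Uric acid prophylaxis rule (6.12.2) | No cycle named |
| Chemistry monitoring (6.12.2, Table 8) | Cycle 1 Day 1, Cycle 1 Day 8, every 3 weeks from Week 4, or more often if indicated |
| Hospitalisation sentence (6.12.2) | Signs tested on Cycle 2 Day 1 |

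In a 21-day cycle, Cycle 2 Day 1 is nominally Day 22. That is 22 − 1 = 21 days after the first dose and 22 − 8 = 14 days after the Day 8 sample. No other provision sets a different time for the hospitalisation step. The narrow reference is therefore unexplained, but nothing contradicts it.

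**The case against.** Three points can be made against the unit finding.

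- **The prefix may be a reading artefact.** The number 476 fits micromol/L, so only one character is in doubt, and a micro sign is easily turned into an m when text is taken from a PDF. Other Greek letters survive in the text, for example in the beta-HCG test and in interferon-gamma, but those are different characters. No micro sign appears elsewhere to serve as a control. This stands, and it makes a check of the source PDF the first step.
- **The two limits are joined by or.** Meeting either one triggers the rule, so a subject above 8 mg/dL qualifies whatever unit the laboratory prints. This stands as a limit on the harm. It does not make the SI figure correct, because a site working in SI units must notice the problem and convert for itself.
- **The error reveals itself.** A limit of 80 g/L is physically impossible, and an attentive physician would probably see that. This also stands as mitigation, but a safety threshold should not depend on it.

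A reader might go further and infer that the section cannot be applied to Cycle 1 laboratory signs, or that the Cycle 2 Day 1 sentence contradicts the rest of the protocol. The protocol supports neither reading. The prophylaxis rule, the hydration advice and the monitoring sentence all operate in Cycle 1. Section 6.5.1 has a general rule for withholding the dose for drug-related toxicities of Grade 3 or greater not listed in Tables 4 and 5. Nothing forbids acting on a Cycle 1 result.

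The passages that seem to place TLS in Cycle 1 do not say so. Section 4.2.3.1 only names "and Grade 3 tumor lysis syndrome" among the exceptions to the DLT definition. Section 2.2.5.1 only reports that for cys-mcMMAF the peak "values were generally observed on Day 2". Neither states when TLS is expected. Whether the named visit is too late is a clinical judgement, outside a statistical review.

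**Conclusion.** The unit error holds, on the text as read. The two versions of the uric acid trigger differ by a factor of 1000 (999.6 to 1000.8 over the molar masses tried), and the SI version is unreachable. The conclusion rests on two assumptions: the molar mass of uric acid, to which it is insensitive, and the unit being printed as mmol/L in the source PDF, which has to be confirmed.

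The practical size is modest because the mg/dL limit beside it remains usable. It would be wrong to infer that subjects with raised uric acid will in fact miss prophylaxis. The protocol shows only that the SI figure cannot identify them. No endpoint, sample size, stopping boundary or DLT classification depends on this cut-off.

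The Cycle 2 Day 1 reference is not a finding. It remains a query, because the section's sole hospitalisation sentence names one visit while fluids and chemistry are already provided for in Cycle 1.

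**What to change.** 1. Check the uric acid unit in Section 6.12.2 against the source PDF. If it is printed as mmol/L, reconcile the two unit versions so that both express the same concentration. The sponsor's clinical team decides what that value is.
2. As a query, ask the sponsor to confirm that the Cycle 2 Day 1 reference in the hospitalisation sentence is as intended, given the fluids before the first dose and the Table 8 chemistry on Cycle 1 Day 1 and Day 8.

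The first is a wording correction and the second needs only an answer. Neither adds a sample, a visit or an analysis.
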